8.1.3 Monitoring Pregnancies for Potential Serious Adverse Events

It is important to monitor the outcome of pregnancies of patients in order to provide SAE data on congenital anomalies or birth defects.

For those participants taking part in the randomised sub-study only, in the event that a female participant of child-bearing potential becomes pregnant during the SAE reporting period, please complete a Pregnancy Notification Form (providing the patient's details) as soon as possible. Provide outcome data on the Pregnancy Notification Form once this is available. If appropriate also complete an SAE Form as detailed in Section 8.3.1.2.

8.2 Reporting Period

The screening procedures for this trial are limited to a review of hospital records, for women of child-bearing potential in the lymphoid cohort who are participating in the sub-study randomisation, a urine dip stick pregnancy test and SAR-CoV-2 antibody level screening for HSCT and CAR-T cell patients only. For all other cohorts SAR-CoV-2 antibody levels have already been assessed outside the study. Hence details of AEs will be documented and reported from the date of re-boost vaccination until 21 days after the administration of the SARS-CoV-2 re-boost vaccination.

SAEs will be captured from consent until 28 days post re- boost vaccination.

SAEs that are judged to be at least possibly related to the IMP and are unexpected must still be reported in an expedited manner irrespective of how long after IMP administration the reaction occurred.

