	
• For the randomised sub-study only, patients who are pregnant or lactating at trial entry or planning to become pregnant within 3 months after re-vaccination.
Blood Sample Collection	Whole blood, serum, plasma, and where possible peripheral blood mononuclear cells (PBMC) will be collected at the following time points: 
• Pre-re-boost vaccine (baseline)• 21 (+14) days post-booster
Trial Duration	Patients are expected to be recruited over 3 months and followed up for 3 months in accordance with standard clinical practice for the relevant disease cohort.
Contacts	
Sponsor: University of Birmingham
 
Chief Investigator: [name], University of Glasgow
 
OCTAVE-DUO Trial Office: Cancer Research UK Clinical Trials Unit (CRCTU), University of Birmingham, [name] ✉ [contact]

SCHEDULE OF EVENTS

	Screening	Trial Entry	Baseline Prior to re- vaccination	Re-vaccination¹	Post-re- vaccination² 21 days post re- vaccination	3-month follow- up Seen in accordance with clinical practice³
Eligibility assessment (including dip stick pregnancy test)	x					
Consent	x					
Measurement of SARS-CoV-2 spike antibody response	(x) ⁴					
Randomisation		x				
Re-vaccination				x		
Data collection		x	x		x	x
Assessment of adverse events					x	
Research blood samples ⁵			X ⁶		x	
Participant Diary Booklet ⁷			x		x	

Key

¹ At least 14 days after receipt of the second dose of vaccine

² Minimum 21 days + 14 days post re-boost vaccination

³ Three months after re-vaccination, where possible data collected retrospectively from participants medical records, telephone follow-up permissible

⁴ For the solid cancer, haematopoietic stem cell transplant and CAR-T cell therapy disease cohorts only: where a result is not available from a previous study or antibodies levels are not available from disease site specific clinics, SARS-CoV-2 spike antibody response can be measured as a screening assessment using one of the assays listed in Appendix 1

⁵ Research blood samples include: Whole blood, serum, plasma, and where possible peripheral blood mononuclear cells (PBMC)

⁶ Research blood sample to be collected -14 to 0 days before re-boost vaccination

⁷ Participant Diary Booklet handed out at baseline and collected at post re-vaccination appointment to aid in collection of Adverse Event (AE) data

[figure not shown]

TRIAL DESIGN

[figure not shown]
[figure not shown]

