7.3.2 Baseline

Participants will be required to attend clinic for the collection of the baseline research sample which must be collected prior to re-vaccination (see Section 7.5 for details of sample collection). Samples can be collected on the day of vaccination as long as this is prior to the re-boost vaccination or up to 2 weeks (14 days) in advance.

The participant should be given a Participant Diary Booklet and instructed on how to complete the diary sheets. Participants should be advised to complete one column per day for 3 weeks. They should be asked to return the Booklet at the day 21 visit.

Data (including medical history, disease history and treatment, prior COVID-19 infection and vaccination history) will be collected on the Baseline Form. These data may be collected retrospectively from the participants' medical records. Where the participant took part in the OCTAVE trial these data will be obtained from the OCTAVE trial database and this information does not need to be provided by the site.

A Research Blood Sample Collection Form should also be completed.

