7.3.4 Post Re-boost vaccination

Participants will be required to attend clinic for the collection of the post re-boost vaccination research blood sample which must be collected on day 21 (as a minimum) or within an additional 14 days (by day 35). See Section 7.5 for details of research blood sample collection.

Participant Diaries should be collected from the participant and used as a guide to complete the Adverse Event Form.

The following forms should be completed at this time point:

- Adverse Event Form
- Research Blood Sample Collection Form

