7.3.5 Three Month Follow-up

Where possible participants will be followed up in accordance with standard clinical practice for the relevant disease cohort and data will be collected retrospectively from clinic records 3 months after re-boost vaccination. Where participants do not attend for a routine clinic visit, data may be collected following an additional telephone follow-up call.

A Follow-up Form should be completed.

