8.3.1.2 Serious Adverse Events

For more detailed instructions on SAE reporting refer to the SAE Form Completion Guidelines contained in the Investigator Site File.

AEs defined as serious that require reporting as an SAE should be reported on an SAE Form. When completing the form, the investigator will be asked to define the causality and the severity of the AE which should be documented using CTCAE version 5.0.

The form should be emailed to the Trial Office as soon as possible and no later than 24 hours after first becoming aware of the event:

Send SAEs to:

[contact]

Cc [contact]

Include "OCTAVE-DUO SAE" in the subject line

On receipt, the Trial Office will allocate each SAE a unique reference number. The site will be informed of the SAE reference number in an email acknowledging receipt of the event. If confirmation of receipt is not received within 1 working day please contact the Trial Office. The SAE reference number should be quoted on all correspondence and follow-up reports regarding the SAE. The email from the Trial Office acknowledging receipt should be filed with the SAE Form in the Investigator Site File.

For SAE Forms completed by someone other than the investigator, the investigator will be required to countersign the original SAE Form to confirm agreement with the causality and severity assessments. The form should then be returned to the Trial Office and a copy kept in the Investigator Site File.

Investigators should also report SAEs to their own Trust or Health Board in accordance with local policy.

Provision of follow-up information

Participants should be followed up until resolution or stabilisation of the event. Follow-up information should be provided on a new SAE Form (refer to the SAE Form Completion Guidelines for further information).

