9 DATA COLLECTION

The CRF will be comprised of the forms listed in Table 2.

Table 2: OCTAVE-DUO Trial Case Report Form

Form	Summary of Data Recorded*	Schedule for Submission to Trial Office
Eligibility Checklist	Confirmation that eligibility criteria are met	Complete at trial entry
Randomisation	Minimal identifiers (initials and date of birth), and stratification factors	Complete at trial entry
Baseline	NHS/CHI/ PROMISE registry ID, hospital number, demographic data (sex, ethnicity), World Health Organisation (WHO) performance status (Appendix 4), body mass index, medical history including comorbidities, disease group specific information (including disease status), and details of prior COVID-19 infection	Within 2 weeks of trial entry
Treatment	Details of rituximab, corticosteroids, and nonsteroidal anti-inflammatory drugs (NSAIDs) and other disease cohort specific treatments	As soon as possible after re-boost vaccination and no later than 2 weeks after trial entry
Vaccination	Date of re-boost vaccination, type of vaccination, batch number (if known)	As soon as possible after re-boost vaccination and no later than 2 weeks after re-boost vaccination
Adverse Event	Details of AEs including date of on-set and grade	No later than 2 weeks after re-boost vaccination
Research Blood Sample Collection	Confirmation of collection of research blood samples in accordance with the protocol	As soon as possible on collection of research blood samples

Form	Summary of Data Recorded*	Schedule for Submission to Trial Office
Follow-up	Survival data, COVID-19 infection data, WHO performance status, disease site specific follow-up information where relevant	Three months post re-vaccination
Death	Date and cause of death	As soon as possible upon notification of participant's death
Withdrawal of Consent	Used to notify the Trial Office of the participant's withdrawal from the trial	As soon as possible upon participant withdrawal
Deviation	Details on deviations from the protocol not captured elsewhere on the CRF	As soon as possible upon discovery of a deviation
Serious Adverse Event	Details of any SAE meeting the definition of an SAE (see Section 8.1.2)	No later than 24h after becoming aware of the event
Pregnancy Notification	Details of any pregnancy which occurs within 3 months of re-vaccination	No later than 24h after becoming aware of the event

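### SAEs are to be captured to day 28, but for a participant seen on day 21 no scheduled contact is stated to ask about days 22–28

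*Protocol*

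**What the plan says.** Section 8.2 of the protocol sets two safety windows. Non-serious adverse events are recorded from re-boost "until 21 days after the administration of the SARS-CoV-2 re-boost vaccination". For serious events the window is longer: "SAEs will be captured from consent until 28 days post" re-boost.

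The planned contacts are these:

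- **Schedule of Events.** The row "Assessment of adverse events" carries a single mark, in the post-re-vaccination column. There is none in the 3-month column.
- **Section 7.3.4.** The post-re-boost blood sample, which defines that visit, "must be collected on day 21 (as a minimum) or within an additional 14 days (by day 35". The forms due at the visit are the Adverse Event Form, completed with the diary as a guide, and the blood sample form.
- **Section 7.3.2.** The diary covers the AE window only: "Participants should be advised to complete one column per day for 3 weeks".
- **Section 7.3.5.** At the next planned contact "data will be collected retrospectively from clinic records 3 months after re-boost vaccination", where possible. A telephone call may be used for those without a routine clinic visit.
- **Section 9, Table 2.** The Follow-up Form is summarised as "Survival data, COVID-19 infection data, WHO performance status, disease site specific follow-up information where relevant".

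SAE reporting itself is triggered by awareness and not by a visit. Under Section 8.3.1.2 the form goes to the Trial Office "as soon as possible and no later than 24 hours after first becoming aware of the event".

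**The concern.** The SAE window is a week longer than the AE window, but no scheduled contact is attached to that extra week. A participant who attends on day 21, the nominal date, hands in a diary that has just ended and has the one scheduled AE assessment. The next planned contact is at 3 months, and the protocol does not say that SAEs are asked about then.

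The exposed events are narrow but real: non-fatal SAEs other than COVID-19 infection, such as an unplanned admission around day 25 to a hospital other than the one running the specialist clinic. Such an event enters the trial record only if the site comes to hear of it. At stake are the completeness of the descriptive safety report and of the SAE listing that the DMC is to review in full (Section 8.3.3.5). One of the vaccines is described as unlicensed in the UK (Section 7.1.3).

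**Working it through.** The protocol gives no figure to reproduce here. The check is date arithmetic plus a comparison of the passages.

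**Inputs**

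- End of the SAE window: day 28 (Section 8.2).
- Permitted visit day, *v*: 21 to 35 (Section 7.3.4).
- End of diary and of AE collection: day 21 (Sections 7.3.2 and 8.2).
- SAE item at 3 months: none in the Schedule of Events and none in the Table 2 summary.

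**Formula.** Days of the SAE window left after the last scheduled AE assessment = max(0, 28 − *v*). Share of the post-dose window = that number ÷ 28.

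| Visit day | Days left | Share of 28 days |
|---|---|---|
| 21 | 28 − 21 = 7 | 7/28 = 25.0% |
| 24 | 28 − 24 = 4 | 4/28 = 14.3% |
| 27 | 28 − 27 = 1 | 1/28 = 3.6% |
| 28 to 35 | 0 | 0% |

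**Average over visit days.** The protocol gives no distribution of visit dates. If visits fell evenly on the 15 whole days from 21 to 35 (an assumption), 7 of 15 visit days (46.7%) would leave a remainder. The mean would be (7+6+5+4+3+2+1)/15 = 28/15 = 1.87 days, and 1.87/28 = 6.7%. The extremes are 0% if every visit is on day 28 or later and 25% if every visit is on day 21.

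**What the table assumes.** It supposes that a visit after day 21 also asks about serious events up to the visit date. No section says so: the visit completes the Adverse Event Form from a three-week diary, and AE collection ends at day 21. If the enquiry is confined to that window, the 7 days apply to every participant whatever the visit date. The firm statement is therefore the one for a day-21 visit: up to 7 of 28 days with no stated scheduled enquiry.

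**What still operates in days 22–28**

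- SAE reporting within 24 hours of awareness (Section 8.3.1.2).
- The Death Form on notification, and survival and COVID-19 infection on the Follow-up Form (Table 2).
- Reporting without time limit of SAEs that are at least possibly related and unexpected (Section 8.2).

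Taking these away leaves non-fatal, non-COVID SAEs that the site does not learn of by itself. The third route also depends on someone hearing of the event.

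**After the fix.** An SAE question reaching to day 28 at the existing 3-month contact brings the remainder to 0 days for every visit date, wherever the 3-month data are obtained.

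**The case against.** The strongest reply is that nothing contradicts itself. The two windows are separate: the single schedule mark and the diary serve the 21-day AE window, while SAE reporting is event-driven and applies throughout. The records review or call at 3 months falls after day 28 and can itself make the site aware of an event, which then triggers an SAE Form. Participants attend specialist clinics, and the GP is told of their participation (Section 5.2). Table 2 gives only a summary of each form. The Follow-up Form and the completion guidelines are not at hand, so a prompt may exist there.

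Most of this stands, and it limits what can be claimed. A reader might infer that days 22–28 are unascertained. They are not: they lack a stated scheduled enquiry, while reporting on awareness, the Death Form and the 3-month survival and COVID-19 items still apply. A reader might also infer that a quarter of SAEs is lost. The 25% is a share of days; the protocol gives no event rate from which to count missed events. Nor do the documents support a claim that comparisons across cohorts or sites are distorted. No such SAE comparison is specified, and the link between coverage and visit date rests on the assumption described above.

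The reply does not supply a planned enquiry. The 24-hour rule governs speed once the site knows; it does not create the knowledge. The 3-month contact may reveal an admission, but neither the schedule nor the form summary directs anyone to look for one.

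**Conclusion.** The point holds in a limited form. The protocol sets an SAE window to day 28, and for a participant seen on day 21 it states no scheduled contact that asks about the last 7 of those 28 days. Non-fatal, non-COVID SAEs in that week depend on spontaneous awareness and may be undercounted. By how much cannot be said, because neither event rates nor visit dates are given.

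The consequence is minor. Safety is an exploratory outcome with descriptive analysis only (Sections 2.2.3.1 and 12.2.4), and the primary immunogenicity outcome is unaffected. A reader might infer a bias between vaccines, but all arms follow the same schedule and nothing in the protocol implies a difference in capture between them. The conclusion assumes that the unseen form and guidelines contain no SAE prompt at 3 months. If they do contain one, the remedy is simply to state it in the protocol. This is a cheap improvement, not a threat to the trial's conclusions.

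**What to change.** Add one yes/no item to the 3-month Follow-up Form and a matching mark in the 3-month column of the Schedule of Events. Suggested content: has the participant had (a) any SAE, as defined in Appendix 2 and not excluded by Section 8.1.2.1, up to day 28 after re-boost that has not already been reported, or (b) any later SAE that is at least possibly related and unexpected, as in Section 8.2? If yes, complete an SAE Form.

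The limits in the wording matter. An open question about any hospital admission would draw in the treatment-related, supportive-care, progression and elective admissions that Section 8.1.2.1 keeps off the SAE Form. Asking about every later event judged possibly related would widen the Section 8.2 rule, which also requires the event to be unexpected.

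The cost is one eCRF item and one schedule mark. No visit, call or sample is added, because the records review or telephone contact is already planned. Some events will reach the Trial Office late, at about 3 months. Participants whose 3-month data are not obtained will still depend on spontaneous reporting.

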8.3 Reporting Procedure

8.3.1 Site

8.3.1.1 Adverse Events

For more detailed instructions on AE reporting refer to the CRF Completion Guidelines contained in the Investigator Site File.

Participants will be provided with a Participant Diary Booklet to aid in the documentation of AEs for up to 21 days post vaccination. The Booklet should be returned at the re-vaccination visit and can be used to facilitate the completion of the Adverse Event Form.

AEs will be graded using the Common Terminology Criteria for Adverse Events (CTCAE), version 5.0 (see Appendix 3).

Any AEs experienced by the participant but not included in the CTCAE should be graded by an investigator and recorded using a scale of (1) mild, (2) moderate or (3) severe.

For each AE, the highest grade should be recorded.

8.3.1.2 Serious Adverse Events

For more detailed instructions on SAE reporting refer to the SAE Form Completion Guidelines contained in the Investigator Site File.

AEs defined as serious that require reporting as an SAE should be reported on an SAE Form. When completing the form, the investigator will be asked to define the causality and the severity of the AE which should be documented using CTCAE version 5.0.

The form should be emailed to the Trial Office as soon as possible and no later than 24 hours after first becoming aware of the event:

Send SAEs to:

[contact]

Cc [contact]

Include "OCTAVE-DUO SAE" in the subject line

On receipt, the Trial Office will allocate each SAE a unique reference number. The site will be informed of the SAE reference number in an email acknowledging receipt of the event. If confirmation of receipt is not received within 1 working day please contact the Trial Office. The SAE reference number should be quoted on all correspondence and follow-up reports regarding the SAE. The email from the Trial Office acknowledging receipt should be filed with the SAE Form in the Investigator Site File.

For SAE Forms completed by someone other than the investigator, the investigator will be required to countersign the original SAE Form to confirm agreement with the causality and severity assessments. The form should then be returned to the Trial Office and a copy kept in the Investigator Site File.

Investigators should also report SAEs to their own Trust or Health Board in accordance with local policy.

Provision of follow-up information

Participants should be followed up until resolution or stabilisation of the event. Follow-up information should be provided on a new SAE Form (refer to the SAE Form Completion Guidelines for further information).

8.3.2 OCTAVE-DUO Trial Office

On receipt of an SAE Form, causality and expectedness will be determined by a Clinical Coordinator. An SAE judged by the investigator or Clinical Coordinator to have a reasonable causal relationship with the trial medication will be regarded as a Serious Adverse Reaction (SAR). If the event meets the definition of a SAR that is unexpected (i.e., is not listed in the Reference Safety Information) it will be classified as a Suspected Unexpected Serious Adverse Reaction (SUSAR).

8.3.3 Reporting to the Competent Authority and Research Ethics Committee

8.3.3.1 Suspected Unexpected Serious Adverse Reactions

The Trial Office will report a minimal data set of all individual events categorised as a fatal or life threatening SUSAR to the MHRA and REC within 7 days. Detailed follow-up information will be provided within an additional 8 days.

All other events categorised as SUSARs will be reported within 15 days.

8.3.3.2 Serious Adverse Reactions

The Trial Office will report details of all SARs (including SUSARs) to the MHRA and REC annually from the date of the Clinical Trial Authorisation (CTA), in the form of a Development Safety Update Report (DSUR).

8.3.3.3 Adverse Events

Details of all AEs will be reported to the MHRA on request.

8.3.3.4 Investigators

Details of all SUSARs and any other safety issue which arises during the course of the trial will be reported to Principal Investigators. A copy of any such correspondence should be filed in the Investigator Site File.

8.3.3.5 Data Monitoring Committee

The independent Data Monitoring Committee (DMC) will review all SAEs.

8.3.3.6 Manufacturer of Investigational Medicinal Product

All SAEs which occur for participant who received the Novavax SARS-CoV-2 vaccine will be reported to the manufacture, Novavax, within 7 days of receipt by the Trial Office.

9 DATA COLLECTION

The CRF will be comprised of the forms listed in Table 2.

Table 2: OCTAVE-DUO Trial Case Report Form

Form	Summary of Data Recorded*	Schedule for Submission to Trial Office
Eligibility Checklist	Confirmation that eligibility criteria are met	Complete at trial entry
Randomisation	Minimal identifiers (initials and date of birth), and stratification factors	Complete at trial entry
Baseline	NHS/CHI/ PROMISE registry ID, hospital number, demographic data (sex, ethnicity), World Health Organisation (WHO) performance status (Appendix 4), body mass index, medical history including comorbidities, disease group specific information (including disease status), and details of prior COVID-19 infection	Within 2 weeks of trial entry
Treatment	Details of rituximab, corticosteroids, and nonsteroidal anti-inflammatory drugs (NSAIDs) and other disease cohort specific treatments	As soon as possible after re-boost vaccination and no later than 2 weeks after trial entry
Vaccination	Date of re-boost vaccination, type of vaccination, batch number (if known)	As soon as possible after re-boost vaccination and no later than 2 weeks after re-boost vaccination
Adverse Event	Details of AEs including date of on-set and grade	No later than 2 weeks after re-boost vaccination
Research Blood Sample Collection	Confirmation of collection of research blood samples in accordance with the protocol	As soon as possible on collection of research blood samples

Form	Summary of Data Recorded*	Schedule for Submission to Trial Office
Follow-up	Survival data, COVID-19 infection data, WHO performance status, disease site specific follow-up information where relevant	Three months post re-vaccination
Death	Date and cause of death	As soon as possible upon notification of participant's death
Withdrawal of Consent	Used to notify the Trial Office of the participant's withdrawal from the trial	As soon as possible upon participant withdrawal
Deviation	Details on deviations from the protocol not captured elsewhere on the CRF	As soon as possible upon discovery of a deviation
Serious Adverse Event	Details of any SAE meeting the definition of an SAE (see Section 8.1.2)	No later than 24h after becoming aware of the event
Pregnancy Notification	Details of any pregnancy which occurs within 3 months of re-vaccination	No later than 24h after becoming aware of the event

This trial will use an eRDC system to capture the CRF data, the only exception to this will be the Eligibility Checklist and SAE Form which will be completed on paper and emailed to the Trial Office.

Access to the eRDC system will be granted to site research staff by the Trial Office.

[**https://www.cancertrials.bham.ac.uk**](https://www.cancertrials.bham.ac.uk)

The investigator and site staff will ensure all data is promptly entered into the eRDC system in accordance with the trial specific User Manual and CRF Completion Guidelines. The CRF must be completed by the investigator or an authorised member of the site research team (as delegated on the Site Signature and Delegation Log).

Entries on the paper CRF should be made in ballpoint pen, in blue or black ink, and must be legible. Any errors should be crossed out with a single stroke, the correction inserted and the change initialled and dated. If it is not obvious why a change has been made, an explanation should be written next to the change.

Data reported on the CRF should be consistent with the source data or the discrepancies should be explained. If information is not known, this must be clearly indicated on the form. All missing and ambiguous data will be queried. All sections are to be completed before returning.

In all cases it remains the responsibility of the investigator to ensure that the CRF has been completed correctly and that the data are accurate.

The CRF may be amended from time to time by the Trial Office throughout the duration of the trial. Whilst this will not constitute a protocol amendment, new versions of the CRF must be implemented by participating sites immediately on receipt.

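### Table 2 makes the Adverse Event Form due by day 14, but AEs are collected to day 21 and the form is completed at the day 21 to 35 visit; pregnancy notification also has two windows

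*Protocol*

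**What the plan says.** **AE Form.** Table 2 in Section 9 lists each form with its schedule for submission to the Trial Office. The Adverse Event Form is due "no later than 2 weeks after re-boost vaccination". Section 8.2 states that "details of AEs will be documented and reported from the date of re-boost vaccination until 21 days after the administration" of the re-boost. Section 7.3.4 puts the post-re-boost sample on day 21 at the earliest and day 35 at the latest. It lists the Adverse Event Form among the forms for that time point and says that "Participant Diaries should be collected from the participant and used as a guide to complete the Adverse Event Form". The Schedule of Events places AE assessment in the post-re-vaccination column only.

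**Pregnancy.** Section 8.1.3, which applies to the randomised sub-study only, asks for a Pregnancy Notification Form as soon as possible if a participant "becomes pregnant during the SAE reporting period". Section 8.2 runs that period from consent to 28 days after the re-boost. Table 2 describes the same form as "Details of any pregnancy which occurs within 3 months of re-vaccination", due within 24 hours of awareness, and does not mention the sub-study.

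**Diary.** Section 7.3.2 says of participants: "They should be asked to return the Booklet at the day 21 visit". Section 7.3.4 and the key to the Schedule of Events agree with this. Section 8.3.1.1 says: "The Booklet should be returned at the re-vaccination visit".

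**The concern.** A form cannot be complete for a 21-day window if it is due on day 14, and a site cannot use a diary that it will not hold until day 21 or later. The protocol does not say that the day-14 submission is provisional. Section 9 in fact asks for every section to be completed before a form is returned. Sites must choose which instruction to follow, and they may choose differently.

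What is at stake is how complete the AE listing is for days 15 to 21. Evaluating the safety of the re-boost is an exploratory objective (Section 2.1.3), reported through a descriptive AE analysis (Sections 2.2.3.1 and 12.2.4), and Section 1 notes that third-dose data are limited. If some sites stopped at day 14, a descriptive table would not show it.

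On pregnancy, the protocol attaches importance to the 3 months after vaccination. Contraception is required for that time in the sub-study (Sections 4.1 and 7.4), and a pregnancy planned within it is an exclusion (Section 4.2). A site reading Section 8.1.3 alone would stop notifying at day 28. Table 2 does not name pregnancy among the contents of the 3-month Follow-up Form, so no other form is stated to pick it up.

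**Working it through.** The plan gives no figure to reproduce. The check sets the stated windows on one time scale, with the re-boost as day 0.

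**AE Form**

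| Item | Source | Day |
|---|---|---|
| AE Form due | Section 9, Table 2 | 14 at the latest |
| AE collection ends | Section 8.2 | 21 |
| Visit at which the form is completed | Section 7.3.4 | 21 to 35 |

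1. Part of the AE window after the deadline: 21 − 14 = 7 days; 7/21 = 33%.
2. Lateness of a form completed at the visit: earliest 21 − 14 = 7 days; latest 35 − 14 = 21 days.
3. At every point in the visit window the lateness is above zero, so a site that completes the form at that visit can never meet Table 2.
4. Conversely, a form sent by day 14 has 14 of 21 days (67%) behind it and is filled in before the scheduled collection of the diary.

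**Pregnancy notification**

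| | Section 8.1.3 with Section 8.2 | Section 9, Table 2 |
|---|---|---|
| Window ends | day 28 | 3 months after re-vaccination |
| Who | women of child-bearing potential in the sub-study | any pregnancy |
| Deadline | as soon as possible | 24 hours after awareness |

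Three calendar months are taken as 90 to 92 days (an assumption, since the protocol does not define them in days). Days covered by Table 2 only: 90 − 28 = 62 to 92 − 28 = 64. With 91 days (13 weeks), 91 − 28 = 63 days = 9 weeks, and 9/13 = 69%. This is calendar coverage. The protocol gives no basis for an expected number of pregnancies.

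**Diary return**

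The Schedule of Events has separate columns for re-vaccination and post-re-vaccination, so Section 8.3.1.1 read literally means day 0. The sentence just before it says that the booklet covers up to 21 days after vaccination. The Schedule key, Section 7.3.2 and Section 7.3.4 all place its return at the later visit. Three places agree, and the fourth does not fit its own preceding sentence.

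**The case against.** The strongest reply is that the Table 2 column governs submission and does not set the period of AE collection. Section 8.2 sets that period expressly as "until 21 days after the administration of the SARS-CoV-2 re-boost vaccination". A site that completes the form at the day 21 to 35 visit is late on paper but loses nothing. Nothing in the protocol says that the electronic form locks once submitted, Section 9 has missing data queried, and Section 10.3 provides central checks for it. This stands. A reader might infer that AEs from days 15 to 21 will be lost, or lost unevenly between sites. The protocol does not support that; it supports only that they could be omitted where a site treats the Table 2 submission as final.

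A reader might also infer from Section 8.3.1.1 that diaries come back empty on vaccination day. That does not hold either. The wording is evidently a slip, contradicted in three other places, and Section 8.1.1 has participants asked about AEs if the booklet is not returned.

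On pregnancy, Section 8.1.3 concerns only women of child-bearing potential in the sub-study, itself a lymphoid malignancy subset of at most 320 participants (Section 12.2.6.2). A site working from Table 2 would notify to 3 months. This limits the number of participants affected. It does not remove the conflict of window, scope and deadline.

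Finally, SAEs have their own form, a 24-hour deadline and a 28-day window (Sections 8.2 and 8.3.1.2), and the Data Monitoring Committee reviews them (Section 8.3.3.5). The AE Form deadline applies equally to all arms, so no bias between arms follows from it. Both points stand, and they keep the weight of this finding modest.

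**Conclusion.** The AE Form conflict is certain on the current text: day 14 in Table 2 cannot be reconciled with collection to day 21 and completion at day 21 to 35. Forms completed as Section 7.3.4 directs are always 7 to 21 days late, assuming the visit falls within its window. The possible loss is confined to AEs from the last 7 of 21 days (33%), and only at sites that take the early submission as final; how many would do so cannot be known from the protocol.

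The pregnancy conflict is equally clear and is secondary: about 9 of 13 weeks rest on one place only, with differing scope and deadline, in a small subset. The diary sentence is an editorial error.

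Overall the consequence is moderate to minor. Safety is an exploratory, descriptive outcome, SAE reporting runs separately, and the primary immunogenicity analysis is untouched. The correction is worth making because the rules cannot all be followed as written and the change costs little.

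**What to change.** 1. **Table 2, Adverse Event Form:** make it due after the post-re-boost visit, for example within 2 weeks of that visit. With the visit on day 21 to 35, the deadline would fall on day 35 (21 + 14) to day 49 (35 + 14), always after the AE window has closed.
2. **Section 8.1.3 and Table 2, pregnancy:** reconcile to one window, one scope (sub-study or all participants) and one deadline. Which window applies is for the sponsor to decide.
3. **Section 8.3.1.1, diary return:** bring the visit named there into line with the Schedule of Events and Sections 7.3.2 and 7.3.4, that is, the day 21 post-re-vaccination visit.
4. **Notice to sites:** state the corrected deadlines. If forms have already been sent in under the day-14 rule, ask those sites to confirm that they were updated after the visit.

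The cost is wording in three places and one notice. No visit, sample or data item is added, and no analysis changes.
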